**Antigen testing:** Instead of detecting viral nucleic acids, the target for antigen tests is the nucleoprotein (N) protein of the SARS-CoV-2 virus. Antigen tests can be performed in a shorter time than PCR tests and are much less expensive. While antigen tests are less sensitive than PCR tests, they both detect individuals who are infectious. The Abbott company developed a very simple assay that has been commercialized for use both as point-of-care as well as an in-home test called the BinaxNOW-COVID-19 Antigen test (hereinafter call BinaxNOW). The test comes packaged within a card which is the size and shape of a credit card and which opens like a small book. In addition, there is a container of reagent. The reagent is delivered into a small hole in the card. A nasal swab is obtained from the patient by swirling the swab gently in the anterior nares several times. The swab is then inserted into the space where the reagent is located and turned several times. A positive test is indicated by the presence of 2 lines, very similar to home pregnancy tests. The testing time is 15 minutes. A positive swab can be detected within 5 to 8 minutes, but the test cannot be classified as negative until 15 minutes have elapsed. In addition, this test is CLIA-waived and can be performed by school health personnel in the school setting, eliminating the need for specimen transport and dramatically reducing turn-around-time and providing immediately actionable results for determining the need for exclusion from school.

The BinaxNOW test is reported to be approximately 94% sensitive in patients with symptomatic COVID-19 infections. Accordingly, it would be anticipated that if an individual who was truly infected with SARS-CoV-2 tested negative with the BinaxNOW test, then another test would almost certainly become positive if repeated within 24 hours, as the climb in viral load is particularly steep once

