### 3.2 Hypotheses to be tested:

**Aim 1.1:** “At-home” BinaxNOW testing will be feasible for families.

**Aim 1.2:** Serial “at-home” BinaxNOW testing is non-inferior to “at school” single PCR testing.

**Aim 2.1:** Lollipop swabs are more acceptable to individuals than nasal swabs.

**Aim 2.2:** Lollipop swabs will perform as well as nasal swabs with PCR-based testing.

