## PROTOCOL TITLE: SAFE AND HEALTHY SCHOOLS

subjects after a single test) versus the alternative hypothesis that the NPV is greater than 91%.

Aim 2: The lollipop swab test will be non-inferior to the gold-standard PCR testing of nasal swabs.

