### 20.2 Sample Size Justification:

For Aim 1, it is anticipated that the majority of initial BinaxNOW tests will be negative. It is hypothesized that the proposed two-day serial testing procedure using BinaxNOW tests in participants with an initial negative test will identify true negatives in >95% of participants. The primary diagnostic outcome measure will be the negative predictive value (NPV). The NPV of BinaxNow is ~91% in symptomatic subjects. For the proposed study, the NPV after the second test (24 hours after the first negative results), is assumed to be substantially higher than 91% since the first test was already negative. In order to detect a true NPV after the second test of at least 95% with 90% power at the one-sided 0.05 significance level, a sample size of N=358 participants with an initial negative test is required. To reach a sample size of N=358 participants with an initial negative test, BinaxNOW kits will be administrated to 400 participants. We intend to continue enrolling until we reach the target sample size of N=358 completing the at-home BinaxNOW test.

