### 20.4 Statistical Methods:

**Aim 1.** Sensitivity, specificity, positive predictive value (PPV) and NPV of the proposed BinaxNOW testing procedure for symptomatic subjects will be calculated and reported along with the corresponding two-sided 95% confidence interval. Formal non-inferiority testing of the BinaxNOW testing procedure with PCR will be conducted with respect to sensitivity and specificity with a non-inferiority margin of  $\delta=5\%$  and a sensitivity/specificity of PCR of 99%.

**Aim 2.** Results obtained from nasal and lollipop swab-based PCR testing will be summarized in tabular format. Concordance between the PCR test results will be evaluated by calculating the Kappa statistic which will be reported along with corresponding two-sided 95% confidence interval. The nonparametric bootstrap technique will be used to construct the confidence interval. A kappa statistic of  $>0.95$  will be considered as sufficient to define lollipop swab test non-inferior to the gold-standard PCR testing of nasal swabs. Furthermore, standard diagnostic test outcomes, i.e., sensitivity, specificity, NPV and PPV will be calculated (using the nasal swab-based

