## 21.0 Potential Benefits to Participants

21.1 For participants who only participate in the lollipop PCR portion of the study, there is no immediate benefit.

Through doing the at-home BinaxNOW testing under the observation of a trained study team member, participants and their families may learn about how to accurately conduct this type of at-home test for COVID-19. Through asking questions and/or receiving confirmation that they are conducting the test correctly, individuals and families may feel more confident conducting at-home tests in the future. If the second test in the BinaxNOW kit is not used as a back-up during the study, the participant may keep the test and use it later if they feel comfortable doing so. The BinaxNOW tests are also readily available to families at local retailers, such as Walgreens. Therefore, if a family member is symptomatic in the future, they may feel more comfortable doing at-home testing independently.

The results of the BinaxNOW test, along with other information, can help participants' healthcare providers make informed recommendations about their care. For example, in the case that the original BinaxNOW and nasal swab PCR tests were negative and the delayed, at-home BinaxNOW test is positive, that would be helpful information for a participant's primary care provider. That information will need to be integrated with the results of the nasal PCR that was also performed. The probability that the delayed, at-home BinaxNOW test will be positive is less than 5%.

If the results of the at-home BinaxNOW test are negative, that may help individuals and families feel more confident in the initial results they received.

The results of the at-home BinaxNOW test in this study, or any future at-home BinaxNOW tests that families may conduct, may help limit the spread of COVID-19 to participants' families and others in their community.

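### Success on the only powered Aim 1 test (NPV above 91%) shows at most an improvement on the cited single-test figure and cannot support the Aim 1.2 claim of non-inferiority to PCR

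*Combined protocol and SAP*

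**What the plan says.** Section 3.2 states for Aim 1.2 that serial home "BinaxNOW testing is non-inferior to" single PCR done at school. Section 20 then gives two rules that could bear on this.

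- **NPV.** Section 20.1 sets 91% as the null boundary, described as the reported rate after a single test in symptomatic subjects, "versus the alternative hypothesis that the NPV is greater than 91" per cent. Section 20.2 names NPV as the primary diagnostic outcome, states that "The NPV of BinaxNow is ~91% in symptomatic subjects", and gives the basis for the size: "In order to detect a true NPV after the second test of at least 95% with 90% power at the one-sided 0.05 significance level". The resulting number is 358 first-test negatives.
- **Sensitivity and specificity.** Section 20.4 adds: "Formal non-inferiority testing of the BinaxNOW testing procedure with PCR will be conducted with respect to sensitivity and specificity", with a 5% margin and PCR taken as 99%. The implied bound is 94%. No sample size is given for this test.

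Sections 5.2 and 20.3, with 20.2, confine the Aim 1 set to people whose first BinaxNOW was negative and who have a home test within 72 hours and a nasal PCR result. No section says which rule decides Aim 1.2, or what follows if NPV succeeds and the 20.4 test does not.

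**The concern.** Everyone in the Aim 1 set has already tested negative once. If the single-test NPV applies to them, the set has an NPV of 91% before the second swab is taken. Exceeding 91% then shows only that the second test finds some of the remaining infections. It does not show that the test finds nearly as many as PCR would.

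This matters because section 2.3 presents the study as a way to lighten the state requirement for PCR after a negative antigen test. If the primary NPV test succeeds and Aim 1.2 is reported as met, schools could read the result as support for dropping PCR, although the home test may have missed more than half of the infections it was meant to catch.

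**Working it through.** **Inputs.** From 20.1 and 20.2: null NPV 91%, alternative 95%, one-sided 0.05, power 90%, N = 358. From 20.4: PCR 99%, margin 5%. From 2.3: reported single-test sensitivity of about 94%. BinaxNOW specificity is not given; 100% is assumed and varied below.

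**1. The plan's sample size.** A one-sample exact binomial test of 0.91 against 0.95 at one-sided 0.05 first reaches 90% power at n = 358. It passes at 335 or more of 358 (93.6%), with exact size 0.0487 and power 0.909. The plan's figure is reproduced.

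**2. Second-test detection implied by an NPV.** Let r be the share of first-test negatives who are PCR-positive, s the share of these found by the second test, and sp its specificity.

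NPV = (1 − r)·sp / [(1 − r)·sp + r·(1 − s)], so s = 1 − (1 − r)·sp·(1 − NPV) / (NPV·r).

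With r = 0.09 and sp = 1:

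| NPV after second test | Meaning in the plan | Implied detection s |
|---|---|---|
| 91% | null | 0% |
| 93.6% (335/358) | smallest pass | 31% |
| 95% | minimum alternative | 1 − 0.91 × 0.05 / (0.95 × 0.09) = 47% |
| 99.4% | NPV at the 20.4 bound: 0.91 / (0.91 + 0.09 × 0.06) | 94% |

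At NPV 95%, specificity of 99%, 97% and 95% gives s = 47.3%, 48.4% and 49.4%. The unknown specificity hardly matters.

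**3. Dependence on r.** At NPV 95%, s is 53% for r = 10%, 39% for r = 8%, 30% for r = 7% and 0% for r = 5%.

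A smaller r is plausible on the plan's other figures. Section 20.2 expects most first tests to be negative. With 94% sensitivity and specificity 100%, at most half positive means prevalence of at most 0.50/0.94 = 53.2%. Then r is at most 0.06 × 0.532 / (0.06 × 0.532 + 0.468) = 6.4%.

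A second test that detects nothing has NPV = 1 − r. Its chance of reaching 335/358 is:

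- r = 9%: 0.049
- r = 6.4%: about 0.57
- r = 5%: 0.909

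**4. What N = 358 can show under 20.4.** Expected PCR-positives are 0.09 × 358 = 32.2. If all 32 are detected, the exact one-sided p-value against 94% is 0.94^32 = 0.138. At least 49 are needed (0.94^49 = 0.048; 0.94^48 = 0.051). The chance of 49 or more among 358 at 9% is about 0.2%. At r = 6.4% only about 23 are expected.

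**5. Denominator.** Strictly, NPV is taken over second-test negatives. At the 95% point that is 358 × 0.91/0.95 ≈ 343, where exact power is about 86% and the smallest pass is 322/343 (93.9%, s about 34%). The conclusion does not change.

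**The case against.** Four objections have force.

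*The 95% is a floor.* Section 20.2 says at least 95% and expects an NPV well above 91%. A reader might infer that the trial is designed for a state in which 20.4 must fail, or that the rationale in 2.3 ("then another test would almost certainly become positive if repeated within 24 hours") is contradicted. The documents do not support that. At the NPV of 99.4% that goes with 94% detection, power is close to 100%. The floor still matters, because the rule passes from 93.6%.

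*The rules are nested.* A second test with 94% detection satisfies the NPV criterion too, so the two standards are not incompatible. One bar is simply far lower than the other. Nor does the plan say outright that NPV success equals non-inferiority: 20.1 speaks only of exceeding the single-test rate, and the formal non-inferiority wording in the Aim 1 methods belongs to sensitivity and specificity. What is missing is the link from these tests to Aim 1.2.

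*The procedure might mean both tests in all symptomatic subjects.* Section 20.4 does refer to the procedure for symptomatic subjects. On that reading, sensitivity at the 95% point would be 0.94 + 0.06 × 0.468 = 96.8%, above 94%. But 5.2, 20.2 and 20.3 restrict Aim 1 to initial negatives. First-test positives do no home test (13.1) and are enrolled to a target of 50 (4.2, 4.3), so the Aim 1 set alone cannot estimate that quantity. The ambiguity is real and 20.4 should resolve it.

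*The 47% depends on 9% residual infection.* It does, and it should not be treated as a fixed property of the plan. A reader might also set it against section 21.1 ("The probability that the delayed, at-home BinaxNOW test will be positive is less than 5" per cent). That conflict arises only if the 9% is imported: at an assumed prevalence of 30%, residual infection is 2.5% and 94% detection gives about 2.4% positives. No change to 21.1 follows from this point.

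**Conclusion.** The point holds. An NPV significantly above 91% shows at most that NPV exceeds the cited single-test figure, and it cannot carry the Aim 1.2 claim. If 91% is the first-test NPV here and specificity is 95–100%, the 95% alternative corresponds to 47–49% detection of the remaining infections, about 45 to 47 points below the 94% bound. With specificity 100%, the smallest pass corresponds to about 31%.

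The exact percentages rest on 9% residual infection, but the direction does not. With less residual infection the NPV test can be passed by a second test that adds nothing; with 10%, implied detection at NPV 95% is 53%, still far below 94%. The comparison with 94% also takes sensitivity in 20.4 to mean the second test among initial negatives, which is the Aim 1 set as defined. The sample-size arithmetic itself is sound.

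**What to change.** 1. In 20.1 and 20.2, state that a significant NPV result may be reported only as NPV above 91%, and that the Aim 1.2 claim of non-inferiority to PCR depends on the sensitivity and specificity criteria in 20.4.
2. In 20.4, state whether sensitivity refers to the second test among initial negatives (the set in 5.2 and 20.3) or to the two-test procedure in all symptomatic subjects. If the latter, say which participants supply the data.
3. Beside the NPV, report the observed second-test sensitivity with its confidence interval and the observed PCR-positive share, so that readers can see what the NPV implies. Do not put a fixed NPV-to-detection table in the protocol, since it would change with the residual infection rate.
4. State that, with about 32 expected PCR-positives, non-inferiority on sensitivity is unlikely to be shown at N = 358, and that the sensitivity result is then an estimate only.

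The cost is wording in the protocol, with no change in N. The price is in the claims: a positive NPV result supports a weaker statement, and on the Aim 1 set as defined the non-inferiority claim will probably remain undemonstrated.

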### 4.2 Number of participants needed to complete the research procedures:

To achieve adequate statistical power, 358 participants with negative at-school BinaxNOW tests need to complete the research procedures, including the at-home BinaxNOW test.

An additional 50 participants with positive at-school BinaxNOW tests need to provide lollipop swabs.

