### 4.3 Replacing enrolled participants:

If participants with negative at-school BinaxNOW test results do not complete the procedures within the target window, i.e., do not successfully completing the at-home BinaxNOW test within 72 hours, they will be replaced. We will continue enrolling until 358

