## PROTOCOL TITLE: SAFE AND HEALTHY SCHOOLS

participants have completed the research procedures within the target timeframe.

We will continue enrolling participants with positive at-school BinaxNOW test results until 50 participants have nasal and lollipop PCR results.

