### 7.5 Compensation:

All participants will be offered a small prize, such as a sticker or small toy, for completing the lollipop swab. All participants who complete an at-school BinaxNOW test will also be given a BinaxNOW COVID-19 Ag Card Home Test kit, which includes two tests and instructions in both English and Spanish. These test kits cost approximately \$20 at local retailers. Participants with a negative at-school antigen test will need to use one of the two tests to complete study procedures. Remaining tests may be used at participants' discretion.

For participants who have a negative at-school BinaxNOW test and therefore complete the at-home BinaxNOW test, this study will provide subjects or their parent/legal guardian, in the case of children, with a \$10 gift card. The gift card will be given to adults after completing the at-home BinaxNOW test. It is possible for people to participate in this research study more than once—they may be eligible each time they get a BinaxNOW test and nasal PCR at school, if they have not had a positive COVID-19 test in the past 3 months. Therefore, participants will be re-consented and compensated each time they participate in the study. If participants do not complete the virtual/home visit, they will not receive a gift card.

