### 20.3 Participant Population for Analysis:

For Aim 1, we will include all participants who complete the at-home BinaxNOW test within 72 hours (N=358) and have nasal PCR results. For Aim2, we will include all participants who have both nasal and lollipop PCR results.

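### N=358 is sized as the number of second-test negatives needed for the NPV test, but enrolment stops at 358 at-home completers of any result, so power at NPV 95% is slightly below the stated 90%

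*Combined protocol and SAP*

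**What the plan says.** Section 20.2 names NPV as the primary diagnostic outcome, takes about 91% as the value after a single test, and targets at least 95% after the second. For 90% power at one-sided 0.05 it concludes that "a sample size of N=358 participants with an initial negative test is required". It plans 400 kits to reach that number and adds "We intend to continue enrolling until we reach the target sample size of N=358 completing the at-home BinaxNOW test".

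The other sections use the same count:
- Section 4.2: "358 participants with negative at-school BinaxNOW tests need to complete the research procedures, including the at-home BinaxNOW test".
- Section 4.3: "We will continue enrolling until 358" "participants have completed the research procedures within the target timeframe" (one sentence, split by a page header).
- Section 20.3, for the Aim 1 analysis set: "we will include all participants who complete the at-home BinaxNOW test within 72 hours (N=358) and have nasal PCR results".

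None of these places sets a condition on the result of the at-home test. The only other statement on that result is in section 21.1, on benefits: "The probability that the delayed, at-home BinaxNOW test will be positive is less than 5" percent. Section 20.4 promises a two-sided 95% interval for NPV but does not name the test for the NPV hypothesis in section 20.1.

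**The concern.** An NPV after the second test is estimated only among people whose second test is negative and who have a reference result. A participant who tests positive at home contributes to sensitivity, specificity and PPV, but not to NPV. If 358 is the number of NPV observations that the power calculation needs, stopping at 358 completers leaves fewer than that. The 400-to-358 allowance covers people who do not complete the at-home test, not those who complete it and test positive.

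What is at stake is whether the 90% power stated for the primary diagnostic measure is delivered at the planned 95%. The validity of the NPV estimate is not in question.

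**Working it through.** **Inputs.** From 20.2: null NPV p0 = 0.91, alternative p1 = 0.95, one-sided alpha 0.05, power 90%, N = 358. From 21.1: at-home positivity below 5%.

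**1. Reproduce 358.**
- Normal formula: n = [(1.645·√(0.91·0.09) + 1.282·√(0.95·0.05)) / 0.04]² = (0.750/0.04)² = 351.6, so 352.
- Exact one-sided binomial test: 358 is the smallest n with power of at least 90%. It rejects at 335 or more PCR-negatives, with attained alpha 0.0487 and power 0.9088.

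The exact test returns the plan's figure, so 358 counts binomial observations of NPV. That the exact test was used is inferred from this match; the plan does not say so.

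**2. Second-test negatives expected from 358 completers.** Suppose 91% of those with a first negative are PCR-negative, the second test gives no false positives, and the NPV after it is 95%. The share negative at home is then 0.91/0.95 = 0.958, so at-home positivity is 4.2%. This gives 358 × 0.0421 = 15.1 positives and 342.9 negatives.

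**3. Power at a true NPV of 95%, no missing nasal PCR.** The second column is averaged over the random number of negatives.

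| Method | 358 negatives | 358 completers, 4.2% positive | Loss (points) |
|---|---|---|---|
| Normal formula | 90.5% | 89.2% | 1.3 |
| Exact test | 90.9% | 87.5% | 3.4, not like for like |
| Exact, smoothed over n ± 12 (around 358 and 343) | 89.0% | 87.8% | 1.2 |
| Randomised exact test, size held at 5% | 91.0% | 89.8% | 1.3 |

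The plain exact comparison overstates the loss because 358 is a peak of a saw-toothed curve: n = 357 gives 86.9% and n = 345 gives 89.9%. Mean attained alpha also falls from 4.9% to 4.0%. The other three rows are like for like. If the 5% ceiling in 21.1 is used as an upper case (358 × 0.95 = 340), their losses rise to about 1.5–1.6 points, hence the range 1.2–1.6.

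**4. When the shortfall disappears.**
- Lower positivity, normal formula: 352 negatives suffice, and 358 − 352 = 6, so positivity up to 6/358 = 1.7% keeps 90%. At 2% the power is 89.9%.
- Higher NPV, keeping the link in step 2: at a true NPV of 95.1% the normal formula gives 90.9%; at 95.2% the averaged exact power is 90.7%.

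**The case against.** **The loss is negligible.** Largely right. By the normal formula the miss is about one point, and section 20.2 hopes for more than 95%. A rise of 0.1–0.2 points in the true NPV restores 90%. What stands is that the plan states its power at 95%, and at 95% it is not met by either method.

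**The number of second-test negatives is not in the documents.** Also right. The 343 is derived and assumes no false positives. Section 21.1 gives only a ceiling. Taking 5% as the expected positivity together with an NPV of 95% would need a split of 4.25% true and 0.75% false positives, which the documents do not give. If the second test catches more of the remaining infections, the denominator falls but NPV rises: 5% positive, all true positives, gives NPV 0.91/0.95 = 95.8% and exact power of about 97%. Positivity well below 4.2%, however, does not fit a planned move from 91% to 95%.

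**All completers might be the intended denominator.** Section 20.2 also speaks of identifying true negatives among participants. But with 91% uninfected, true negatives cannot exceed 91% of all completers, so a 95% target makes sense only among second-test negatives.

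**Stronger readings.** A reader might infer that Aim 1 is underpowered by three to four points, or that enrolment must rise. The first mixes discreteness with the real loss. The second depends on a test that the plan does not name, and the size of the shortfall does not require it. Repeat participation (section 7.5) is a separate matter whose effect cannot be sized from the documents.

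**Conclusion.** The mismatch is real and its effect is small. The figure of 358 was derived for second-test negatives with a PCR result but is applied to all at-home completers. Power at a true NPV of 95% is about 89% (normal) or 87–88% (exact) instead of 90%.

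This rests on a 91% PCR-negative base, no false-positive second tests, independent observations and no missing nasal PCR. Section 20.3 requires a nasal PCR result whereas the stopping rule in 20.2 does not, so missing results would lower the count further by an amount that the documents do not allow one to compute. Analysing all completers remains right for sensitivity and specificity; only the NPV count and its stated power need correction. This is worth correcting but does not threaten the design.

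**What to change.** In sections 4.2, 20.2 and 20.3, state that the NPV denominator is second-test negatives with a nasal PCR result, and that 358 completers are expected to give about 343 of them if 4.2% are positive at home with no false positives. In 20.4, name the test for the NPV hypothesis. In 20.2, restate the power at NPV 95% under that test: about 89% for a normal-approximation test, or about 87–88% for the exact binomial test.

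The cost is wording only, with no change to enrolment, procedures or data collection. The price is a stated power slightly below 90%.
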